14.1 Sample Size Determination

Based on data from Stony Brook and confidential data HeartFlow reported from providers who have been using CT-FFR in a similar manner as we propose for this study, we estimated that about 60% of stable chest pain patients who had CCTA were diagnosed with coronary stenosis of 30% to 90% and received CT-FFR. Of these patients, about 35% had an ICA test, and 14% of those had a negative ICA test result (i.e. the false-positive rate of CCTA+CT-FFR was 14%). A sample of 121 patients who received ICA will yield 80% statistical power of detecting a 60% reduction in the false-positive rate (from 14% to 6%), based on a two-sided one sample Chi-square test with 0.05 significance level. Assuming a similar prevalence of flow-limiting obstructive CAD and assuming that similar proportions of stable chest pain patients who had CCTA will receive CCT-FFR and then ICA, 576 stable chest pain patients who had CCTA need to be complete the clinical trial. In order to target 576 subjects completing the trial, we estimate that number of patients, it will be necessary to 594, because 18 patients who enrolled were screen failures.

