In order to assess the primary endpoint of comparison of event rates for patients treated with CCTA and FFR-CT, we will perform a retrospective chart review of Invasive Coronary Angiograms performed at Lenox Hill Hospital from 2014 to 2018. We will specifically review Cardiac Catheterization reports to screen patients and record data for cases where the indication for Catheterization was (1) Positive stress test and/or (2) Positive CCTA. Based on the catheterization report we will determine whether the patient had obstructive coronary artery disease with/without flow limitation, in the same manner and following the same definitions as those used to categorize level of obstruction in subjects enrolled in the prospective cohort of the study. This data will be used as comparison/control group to assess trends and rates of invasive coronary catheterization when no intervention is necessary, in cases where CCTA and/or stress test without CT-FFR was used to determine the need for cardiac catheterization. Only the minimum amount of data required for a robust comparison of event rates will be collected.

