6.2 Primary Study Endpoints

Defining an event as performance of ICA when no intervention is necessary, we expect to compare event rates for patients treated with CCTA and FFR-CT, using t-tests and a multivariate, risk adjusted 90 day hazard model with 95% confidence interval. Our null hypothesis is that outcomes will not vary regardless of which testing is used to assess

obstructive disease. Our alternative hypothesis is that evaluation with FFR-CT as oppose to CCTA will change the event rate. We will also correlate noninvasive and invasive FFR studies.

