7.5 Consent Process

The study cardiology fellow or cardiologist will obtain the informed consent from the patient in the Lenox Hill Ambulatory CCTA Clinic. An attempt at outreach will be made for scheduled patients to apprise them of the fact that a study is being conducted. Consent will be obtained on the days of the study. Before consent is obtained, the cardiologist or cardiology fellow will review the major activities of the study with the patient, provide an opportunity for the patient to ask questions, and ask the patient to sign the consent. The patient will receive a copy of the informed consent form (attached), explaining the procedure. Signed informed consent forms will be maintained by the Study Coordinator.

We would like to request a waiver of consent and HIPAA Authorization for the retrospective chart review portion of the study. There will be no intervention, testing, or contact with subjects included in this portion. Only the minimum amount of data required for a robust comparison of event rates will be collected. The retrospective portion of the study meets the criteria for a complete waiver of consent 1) The research involved no more than minimal risk as it simply involves the collection and analysis of previously collected health information of patients who underwent CCTA and invasive cardiac catheterization. 2) The waiver will not adversely affect the rights or welfare of participants because, given that the research would

not impact the participant's current or future care; 3) the study could not be practicably conducted without the waiver given the large sample size and the fact that the participants were never or are no longer patients of the PI. It is also possible that the subjects are now deceased or no longer part of the Northwell system. 4) The outcome of the chart review will not impact the future care of participants so no additional information will be provided to them. The study will protect the identifiers by storing information in REDCap.

PHI (date of procedure and participant name) is required for the conduct of the retrospective portion of the study as the researchers will need to access the charts of individuals who meet study criteria in order to collect the test results of interest.

No study participants under the age of 18 will be recruited.

Cognitively impaired subjects will not be recruited, due to the need for the subjects to be capable of following the technologist's instructions during the CCTA exam.

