In order to assess the primary endpoint of comparison of event rates for patients treated with CCTA and FFR-CT, we will perform a retrospective chart review of Invasive Coronary Angiograms performed at Lenox Hill Hospital from 2014 to 2018. We will specifically review Cardiac Catheterization reports to screen patients and record data for cases where the indication for Catheterization was (1) Positive stress test and/or (2) Positive CCTA. Based on the catheterization report we will determine whether the patient had obstructive coronary artery disease with/without flow limitation, in the same manner and following the same definitions as those used to categorize level of obstruction in subjects enrolled in the prospective cohort of the study.

This data will be used as comparison/control group to assess trends and rates of invasive coronary catheterization when no intervention is necessary, in cases where CCTA and/or stress test without CT-FFR was used to determine the need for cardiac catheterization. Only the minimum amount of data required for a robust comparison of event rates including the following identifiers -name, date of procedure and age will be collected.

9.1 Visit 1

1. Visit 1 is an ambulatory visit to Lenox Hill Outpatient CCTA Clinic. Consent for study participation will be collected and routine CCTA will be administered.

9.2 Visit 2

If CCTA shows < 30% obstruction, visit 2 will be a referral for optimal follow-up cardiac care. If CCTA shows 30 to 49% obstructive disease and CT-FFR is negative, visit 2 will be a referral for optimal follow-up care.

If CCTA shows 50% to 70% obstructive disease and CT-FFR is negative, visit 2 will be a referral for Stress MPI testing.

If stress testing has been performed in the past year, then the results of those test will be considered, and new stress testing will not be performed.

If prior stress test was negative, visit 2 will be a referral for optima follow-up cardiac care.

If the investigator assessed that the prior stress test results increase the risk of acute obstructive cardiac disease for the patient, Visit 2 will be a referral to cardiac catheterization and invasive FFR.

If CCTA shows $\geq 70\%$ obstructive disease visit 2 will be referral to cardiac catheterization and invasive FFR.

If CT-FFR is positive, visit 2 will be a referral to cardiac catheterization and invasive FFR.

9.3 etc.

Visit 3:

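### The 80% power in 14.1 is for a one-sample test against a fixed 14%, whereas the primary comparison is with a chart-review control of unstated size, and the 14% is labelled as the rate of the strategy under test

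*Combined protocol and SAP*

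**What the plan says.** Section 14.1 draws on Stony Brook data and on confidential vendor data from providers already using CT-FFR. It takes 60% of CCTA patients as receiving CT-FFR and 35% of those as having ICA, and then states "14% of those had a negative ICA test result (i.e. the false-positive rate of CCTA+CT-FFR was 14" per cent). From this it claims 80% power with 121 ICA patients for "detecting a 60% reduction in the false-positive rate (from 14% to 6" per cent), "based on a two-sided one sample Chi-square test with 0.05 significance level". It scales up to 576 completers, "assuming that similar proportions of stable chest pain patients who had CCTA will receive CCT-FFR and then ICA".

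Section 6.2 defines the primary event as an ICA when no intervention is needed, and plans to "compare event rates for patients treated with CCTA and FFR-CT, using t-tests and a multivariate, risk adjusted 90 day hazard model". Section 6.1 says of the 2014-2018 chart review: "This data will be used as comparison/control group to assess trends and rates of invasive coronary catheterization when no intervention is necessary". Section 9 repeats this and adds "in cases where CCTA and/or stress test without CT-FFR was used to determine the need for cardiac catheterization".

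No section gives the number of chart-review ICAs. The only remark on size is in 7.5, in the waiver request: "the study could not be practicably conducted without the waiver given the large sample size". Section 14.2 covers diagnostic accuracy, reader reliability and return visits. It contains no analysis against the control group.

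**The concern.** There are two separate problems with the only power statement in the plan.

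- **Test.** A one-sample test treats the comparison rate as a known constant. The primary comparison estimates that rate from a sample of charts, so it has sampling error that 14.1 leaves out. How much this matters depends on the number of charts, which is not stated.
- **Label.** The 14% is the rate to be reduced, so it should describe patients evaluated without CT-FFR. The text calls it the rate with CT-FFR. If the label is a slip, the control rate is mislabelled. If the label is right, the plan gives no expected control rate.

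As it stands, a reader cannot attach a power figure to the primary comparison, or say with certainty which two rates the investigators expected to differ. That weakens the reading of a null result in particular.

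**Working it through.** **1. Reproduce the plan's figure.** Inputs from 14.1: p0 = 0.14, p1 = 0.06, two-sided alpha 0.05, power 0.80.

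n = [1.96·√(p0(1−p0)) + 0.8416·√(p1(1−p1))]² / (p0−p1)² = [1.96·√(0.14·0.86) + 0.8416·√(0.06·0.94)]² / 0.08² = 120.99, so 121.

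Exact power of this one-sample test at n = 121 is 80.9%. Completers: 121/(0.60·0.35) = 121/0.21 = 576.2. Both stated figures reproduce for the one-sample test.

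**2. Which pathway does the 14% describe?**

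- Section 3.4 reports a 54% reduction in the false-positive rate with CT-FFR compared with CCTA alone. Applied downward, 0.14·(1−0.54) = 6.4%, close to the planned 6%. This favours 14% as the rate *without* CT-FFR, with the label a slip.
- Applied upward, 0.14/0.46 = 30.4%. That would be the control rate if the label is right.
- Section 14.1 cites both Stony Brook and CT-FFR providers. Section 3.4 dates the Stony Brook programme from January 2009 to March 2015, and 3.2 dates FDA approval of CT-FFR to November 2014. A blend of pathways is therefore also possible.

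**3. Two-sample power, 14% as control rate and 6% with CT-FFR.** 121 prospective ICAs; pooled z-test of two proportions, two-sided 0.05, exact binomial enumeration. Control sizes are assumptions.

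| Chart-review ICAs | Power |
|---|---|
| 121 | 56% |
| 500 | 72% |
| 1,000 | 76% |
| 2,000 | 78% |
| 5,000 | 79.5% |

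As the control grows without limit, power tends to the one-sample value of 80.9%. The 121-chart row is unlikely, given the remark on size in 7.5.

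**4. Effect of the test.** Section 6.2 names t-tests without saying which. An equal-variance t-test gives the same figures as the table. An unequal-variance t-test gives 82%, 86% and 88% with 500, 1,000 and 2,000 charts. Its actual type I error at 14% against 14% is 5.3%, 5.6% and 5.7%, so part of that gain comes from exceeding the nominal level.

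**5. Two-sample power, 14% as the CT-FFR rate.** With a control rate of 30.4% (illustration only), pooled power is 88% with 121 charts, 98% with 500 and 99% with 1,000. With 500 to 2,000 charts, 80% power needs a control rate of about 25%.

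**6. Limits.** All these figures are unadjusted and ignore the risk-adjusted model in 6.2. Step 3 also assumes that 14% describes the control actually reviewed. By 6.1 and 9, that control includes ICAs referred on a positive stress test alone, and nothing in 14.1 shows that the 14% covers that mix.

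**The case against.** The strongest reply is that a large historical control makes a fixed benchmark a fair approximation. With 14% as the control rate, the pooled test has 78% power at 2,000 charts and 79.5% at 5,000, and 7.5 does suggest many charts. This stands as far as it goes: the gap is then small. It does not supply the missing control size, and it leaves the label untouched.

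A second reply is that the one-sample calculation suits Aim 1 in 14.2, a single-cohort accuracy estimate in which the negative-ICA proportion is one minus the PPV. That is a fair account of where the calculation may have come from. However, 6.1 and 9 tie the primary endpoint to the control group.

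Third, 14.1 speaks of 18 enrolled patients who were screen failures, so enrolment had begun and a revised statement may document more than it decides. This is a good reason to keep the remedy to text.

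Two stronger readings should be resisted. A reader might infer that the trial is underpowered. The documents do not support this, because power runs from somewhat below to well above 80% depending on the control size, the test and the meaning of the 14%. A reader might also infer that no expected control rate is given at all. That holds only if the label is correct; on the likelier reading, the 14% is that rate. The gap between 60% and 57% (1−6/14) is rounding, since 121 fits 6%.

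**Conclusion.** The point holds, as one that should be fixed. The plan's 80% power is correct for a one-sample test of 6% against 14%, but the primary comparison is with a sampled control of unstated size. The 14% is labelled as the CT-FFR rate while serving as the rate to be reduced. The label is more likely a slip than not, though the text leaves open that 14% is the CT-FFR rate or a blend.

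On the likelier reading, with an assumed 500 to 2,000 charts, unadjusted power is 72% to 78% with a pooled test and 82% to 88% with an unequal-variance t-test. If 14% is the CT-FFR rate and the control rate is near 30%, it is 98% or more with 500 charts or more. The direction of the error in the stated 80% therefore cannot be determined from the documents. The defect is a power statement that does not match the comparison, not a demonstrated shortage of patients.

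**What to change.** In 14.1:

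1. State which pathway the 14% describes, and correct the label if it is a slip.
2. State the expected negative-ICA rates with and without CT-FFR, each with its source, for the control mix actually reviewed (CCTA and/or stress-test referrals).
3. State the number of chart-review ICAs.
4. Replace the one-sample statement with a two-sample one for the test used in 6.2, which should say which t-test (or other test) is meant. For example: *With about 121 prospective ICAs and m chart-review ICAs, a two-sided unadjusted comparison of x% with y% at the 0.05 level has z% power; the risk-adjusted model in 6.2 is not reflected in this figure.* For orientation, z is about 76 with an assumed m of 1,000, 14% against 6% and a pooled test.

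Minor tidying: give the effect as 14% to 6% (57%), and carry one sample size through the Study Summary, Section 5, 6.1 and 14.1, which now give 572 in the first three and 576 completers (594 enrolled) in the last.

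The cost is a recalculation, text edits and a count of eligible charts. It needs no new data from enrolled patients and no change in enrolment. The downside is that the stated power may fall a few points below 80%.

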14.2 Statistical Methods

Statistical Aims

1. *To determine the sensitivity, specificity, positive predictive value (PPV) and negative predictive value (NPV) of the CCTA test (with or without stress MPI, as specified in Figure 1) + CT-FFR evaluation to identify chest pain patients with flow-limiting obstructive CAD. The ICA test will be used as gold standard.*
2. *To determine inter-observer reliability of CCTA and CCTA+CT-FFR test readings between an experienced and a non-experienced reader, and compare the results between CCTA and CCTA+CT-FFR; to determine the intra-observer reliability of CCTA and CCTA-FFR reading, for both the experienced and non-experienced reader, and for each reader compare the results between CCTA and CCTA+CT-FFR.*

3. To identify factors of return visit within 90 days in patients who had no ICA test or a negative ICA test result.

Outcome Variables

- *CCTA+CT-FFR test status (Positive/Negative). The test is deemed positive if ICA is required and negative if ICA is not required (see Figure 1).*
- *ICA (gold standard) test status (Positive / Negative). ICA is deemed positive if $FFR < 0.8$ and vessel diameter $>= 2\text{mm}$ or if the patient requires revascularizations based on invasively estimated stenosis severity. It is deemed negative otherwise.*
- *Return visit within 90 days (Y/N). Return visit is defined as patients who return for unplanned cardiac care, including emergency room visits, emergency hospital admissions, urgent percutaneous coronary intervention, coronary artery bypass graft, or acute myocardial infarction. Descriptive statistics (n, mean, median, standard deviation, IQR, frequencies and percentages) will be used to describe the demographic and clinical characteristics of the whole sample.*

For Aim 1, sensitivity, specificity, PPV, and NPV will be computed using the ICA result as the ‘true’ flow-limiting obstructive CAD status and the CCTA+CT-FFR test result as the ‘test’ status. Exact binomial 95% confidence intervals will be computed.

For Aim 2, inter- and intra-observer reliability for the CCTA and CCTA+CT-FFR tests will be assessed using Cohen’s Kappa coefficient. Dependent Kappa coefficients will be compared using a method developed by Donner et al .

For Aim 3, a survival analysis regression model will be carried out to determine which risk factors are associated with “time-to-return visit”. Proposed factors will include age, sex, race, diabetes, hyperlipidemia, hypertension, active smoking and smoking history, family history of premature heart disease, obesity, and the number of cardiac risk factors present. In addition we will consider adding whether the admission was surgical or medical, and the MS or AP DRG case weight as a measure of severity.

Statistical Methods

Descriptive statistics (n, mean, median, standard deviation, IQR, frequencies and percentages) will be used to describe the demographic and clinical characteristics of the whole sample.

For Aim 1, sensitivity, specificity, PPV, and NPV will be computed using the ICA result as the ‘true’ flow-limiting obstructive CAD status and the CCTA+CT-FFR test result as the ‘test’ status. Exact binomial 95% confidence intervals will be computed.

For Aim 2, inter- and intra-observer reliability for the CCTA and CCTA+CT-FFR tests will be assessed using Cohen’s Kappa coefficient. Dependent Kappa coefficients will be compared using a method developed by Donner et al .

For Aim 3, a survival analysis regression model will be carried out to determine which risk factors are associated with “time-to-return visit”. Proposed factors will include age, sex, race, diabetes, hyperlipidemia, hypertension, active smoking and smoking history, family

history of premature heart disease, obesity, and the number of cardiac risk factors present. In addition we will consider adding whether the admission was surgical or medical, and the MS or AP DRG case weight as a measure of severity.

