Coronary Computed Tomography Angiogram (CCTA) is a non-invasive imaging modality that has high sensitivity and negative predictive value for the detection of coronary artery disease (CAD). The main limitations of CCTA are its poor specificity and positive predictive value, as well as its inherent lack of physiologically relevant data on hemodynamic significance of coronary stenosis, a data that is provided either by non-invasive stress tests such as myocardial perfusion imaging (MPI) or invasively by measurement of the Fractional Flow Reserve (FFR). Recent advances in computational fluid dynamic techniques applied to standard CCTA are now emerging as powerful tools for virtual measurement of FFR from CCTA imaging (CT-FFR). These techniques correlate well with invasively measured FFR [1-4]. The primary purpose of this study is to evaluate the incremental benefit CT-FFR as compared to CCTA in triaging chest pain patients in outpatient settings who are found to have obstructive CAD upon CCTA (> 30% stenosis). Invasive FFR and short term clinical outcomes (90 days) will be correlated with each diagnostic modality in order to evaluate positive and negative predictive value of each when used incrementally with CCTA.

Patients will undergo a CCTA, as part of routine care. If the patient consents to participate in the study and is found to have coronary stenosis of 30% to 100%, based on the cardiologist's reading, the CCTA study will be sent to HeartFlow, a vendor that will provide a computerized FFR reading, based on the CCTA study. If the noninvasive FFR diagnosis indicates obstructive disease, the patient will undergo cardiac catheterization with invasive FFR.

As CCTA utilization increases, the need to train additional imaging specialists will increase. This study will assess the capability of FFR-CT to enhance performance on both negative and positive predictive value for less experienced readers by providing feedback based on CT-FFR evaluation. CCTA readers will be grouped in two categories: those with more than 10 years reading experience and those with less than 10 years reading experience. Each CCTA will be read by a less experienced and a more experienced reader. Results from each reader will be correlated with each other and with the CT-FFR and invasive FFR results.

3 Introduction

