6.1 General Design

This will be a prospective clinical trial designed to evaluate the incremental benefit of virtual FFR measured from CCTA, compared to invasive FFR and CCTA for the detection of flow-limiting coronary stenosis, as defined by invasive FFR ≤ 0.8 and vessel diameter of $\geq 2\text{mm}$.

572 consecutive patients who present to Lenox Hill Hospital Outpatient Clinics for CCTA due to chest pain or stable angina over a ten month period and meeting the study inclusion criteria are eligible for the study (Figure 1). Our team will employ CCTA-appropriateness criteria to ensure proper selection of patients, derived from the Appropriate Use Criteria for Cardiac Computed Tomography published in 2010 and jointly authored by multiple societies including ACCF, SCCT, and ACR [10]. FFR-CT measurements will be performed by a core laboratory in a blinded fashion. All eligible patients will undergo 64-slice or greater multi detector CCTA and CT-FFR measurements. The severity of the stenosis will be determined on site by level III CCTA readers. Patients with obstructive lesions of (30% to 100% stenosis) will receive Stress-MPI, per SOC protocol, and CT-FFR. Patients with positive Stress-MPI and CCTA (50% - 70%) or positive CCTA (71% to 100%) will undergo ICA with invasive FFR measurement in accordance to accepted guidelines and established practice standard. Those patients with invasively measured FFR ≤ 0.8 and with vessel diameter of $\geq 2\text{mm}$, or those who require revascularizations based on invasively estimated stenosis severity will be considered to have flow-limiting obstructive CAD, while the rest will be considered to have non-flow limiting obstructive CAD (if also $>50\%$ stenosis on ICA). If stenosis severity turns out to be $< 50\%$ after ICA (the gold standard), we will conclude that these patients have non-obstructive CAD. (Figure 1). Patients with 30% to 49% obstructive disease, according to CCTA, will be referred to optimal follow up care only. Any in this group who have positive CT-FFR will return for

ICA with invasive FFR measurement, and follow the protocol for those with 50% to 100% obstruction.

Figure 1:

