8.3 Method for Assigning Subjects to Treatment Groups

This is not a randomized study. Treatment assignments will follow the clinical protocol.

Once the CCTA results are interpreted by the physician, the physician will order CT-FFR exams for patients whose level of stenosis by CCTA standards is 30% to 100%.

If CT-FFR is positive patients will be referred for Cardiac Catheterization and invasive FFR.

If CT-FFR is negative, and level of obstruction is 30 to 49% by CCTA standards, patients will be referred to optimal medical care.

If CT-FFR is negative and level of obstruction is 50% to 70% by CCTA standards, patient will be referred for stress MPI. If stress MPI is positive patients will be referred for Cardiac Cath and invasive FFR. If stress MPI is negative, patients will be referred to optimal medical care.

If the patient has had a stress MPI within one year of the CCTA exam and the CCTA exam result is 50% to 70% obstructive, the physician will rely on the prior stress testing result, rather than repeating the stress test. If the stress testing results was negative, the patient will be referred to optimal medical care. If, in the investigator's opinion, the results indicate that the patient is at increased risk of obstructive disease, when considered with the CCTA findings, the patient will be referred to Cardiac Cath and Invasive FFR.

If CT-FFR is negative and level of obstruction is 70% to 100% by CCTA standard, patient will be referred to Cardiac Cath and Invasive FFR.

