15.4 Unblinding Procedures

This is not a blinded clinical trial. Blinding in this study will not affect patient outcome, and, therefore, no unblinding is necessary. Cardiologists will interpret CCTA scans without access to FFR results. This is standard of care, and the interpretation will be necessary to determine which cases should be sent for FFR. The FFR is a computerized procedure. At the time the procedure is run, the computer operator will not know the exact level of obstruction documented by the cardiologist. This information is irrelevant to the operations of the computerized procedure and will not change the outcome of the CT-FFR test or the follow up patient care.

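### Aim 2: a higher kappa for CCTA+CT-FFR than for CCTA describes the combined test; it is not evidence that CT-FFR helps less experienced readers

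*Combined protocol and SAP*

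**What the plan says.** Section 2 sets up two reads per scan: "Each CCTA will be read by a less experienced and a more experienced reader". Sections 8.8 and 15.4 have the CCTA read without sight of CT-FFR. Section 14.2, Aim 2, then assesses "inter-observer reliability of CCTA and CCTA+CT-FFR test readings between an experienced and a non-experienced reader" by Cohen's kappa, does the same within each reader, and adds: "Dependent Kappa coefficients will be compared using a method developed by Donner et al".

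The combined result is defined by its consequence (Section 14.2, Outcome Variables): "The test is deemed positive if ICA is required and negative if ICA is not required". Section 8.3 supplies the consequence: "If CT-FFR is positive patients will be referred for Cardiac Catheterization and invasive FFR". A negative CT-FFR does not settle the matter in the same way. At 30–49% there is no ICA. In the next band, "If CT-FFR is negative and level of obstruction is 50% to 70% by CCTA standards, patient will be referred for stress MPI". In the highest band the patient still goes to ICA.

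CT-FFR itself is a single computation per scan. Section 6.1: "FFR-CT measurements will be performed by a core laboratory in a blinded fashion". Section 15.4: "The FFR is a computerized procedure". Section 9 adds that a physician interprets the vendor's output. Section 6.3 speaks of the two reader cohorts' readings of both CCTA and CT-FFR. No section says whether the positive or negative CT-FFR call is made once per scan or by each reader.

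The Study Summary and Sections 2 and 4 state the reader objective: better positive and negative predictive value for less experienced readers, through feedback from CT-FFR.

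**The concern.** The two kappas being compared do not contain the same ingredients. The CCTA kappa rests on two separate stenosis readings. The combined kappa rests on those readings plus a CT-FFR computation common to both readers, which can decide the result for both at once. Part of any difference can therefore come from the scoring rule and not from the readers. The same applies to the intra-observer comparison, where one reader meets the same computation twice.

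This matters because Aim 2 is the only statistical aim that separates readers by experience. Aim 1 computes PPV and NPV for the pathway as a whole, not by reader. A rise in kappa would be the natural number to set against the less-experienced-reader objective, and it cannot carry that conclusion. A test for dependent kappas allows for the correlation between the two estimates. It does not remove a component that both readers share in only one of them.

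**Working it through.** **1. The plan's own figures.** Section 14.1 gives the only sizing. With 14% against 6%, two-sided 0.05 and 80% power, n = [1.960·√(0.14·0.86) + 0.842·√(0.06·0.94)]² / 0.08² = 120.99, so 121; and 121/(0.60·0.35) = 576.2, so 576. Both reproduce. Neither concerns Aim 2, which has no expected kappa, alpha or power. Two inputs carry over. About 0.60·576 = 346 scans would have CT-FFR, and about 35% of those go to ICA. Since every positive CT-FFR is referred to ICA, CT-FFR positivity should not exceed about 35% (121 scans) if referrals are followed, which leaves at least about 225 negative.

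**2. Where the two results can differ** (Section 8.3, both readers calling at least 30%):

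| CT-FFR | Combined result for each reader | Effect on disagreement |
|---|---|---|
| Positive | Positive, whatever the stenosis band | Removed, if the call is shared |
| Negative | Decided by the reader's own band, with stress MPI at 50–70% | Unchanged |

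The whole difference therefore arises in CT-FFR-positive scans.

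**3. Counts.** With equal marginals, kappa = 1 − D/[2q(1−q)], where D is the discordant share and q the positive share. Take 200 scans with assumed counts and make 60 of them CT-FFR-positive, readers unchanged. Triples are both positive / both negative / discordant.

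| 60 scans drawn from | Resulting table | q | kappa |
|---|---|---|---|
| (none: CCTA alone) | 50 / 100 / 50 | 0.375 | 0.467 |
| 45 / 10 / 5 | 65 / 90 / 45 | 0.438 | 0.543 |
| 15 / 30 / 15 | 95 / 70 / 35 | 0.563 | 0.644 |
| 25 / 10 / 25 | 85 / 90 / 25 | 0.488 | 0.750 |

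These positive shares exceed the planned 35%, so the table shows direction only.

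**4. Anchored to 35%.** Let p be the CCTA-positive share, k the CCTA kappa, and t the CT-FFR-positive share, assumed independent of the reads. Then D becomes (1−t)D and 1−q = (1−t)(1−p), which gives 1−k′ = (1−k)·p/q. Set q = 0.35, so t = 1 − 0.65/(1−p):

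| p | t | k = 0.40 becomes | k = 0.60 becomes |
|---|---|---|---|
| 0.20 | 0.19 | 0.66 | 0.77 |
| 0.25 | 0.13 | 0.57 | 0.71 |
| 0.30 | 0.07 | 0.49 | 0.66 |

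**5. Why a rise is not certain.** Take p = 0.50 with 10% disagreement (kappa 0.80). Suppose CT-FFR is positive in every agreed positive, in no discordant scan, and in agreed negatives amounting to 30% of all scans. Then q = 0.45 + 0.05 + 0.30 = 0.80 and kappa = 1 − 0.10/(2·0.80·0.20) = 0.69. This is an extreme pattern, but it shows that the rule alone does not force a rise.

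Separate interpretation matters more. A simulation of the Section 8.3 pathway used 1,000,000 scans and these assumptions: true stenosis <30 / 30–49 / 50–70 / 71–100% in 40/30/20/10% of scans; reader SD 10 and 15 points; CT-FFR positive in 3/15/40/70% and MPI positive in 5/10/30/60% by band. Reader skill was fixed and the MPI result shared.

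| Each reader's CT-FFR interpretation error | CCTA with or without MPI | Combined, CT-FFR counted only if that reader calls ≥30% | Combined, CT-FFR counted for both |
|---|---|---|---|
| None (identical call) | 0.64 | 0.77 | 0.82 |
| 5% | 0.64 | 0.68 | 0.70 |
| 10% | 0.64 | 0.59 | 0.60 |
| 20% | 0.64 | 0.45 | 0.43 |

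(The CCTA kappa varied from 0.643 to 0.645.) With an identical call, the gain ran from +0.08 to +0.23 across the scenarios tried. In the variant where CT-FFR is rarely positive at 30–49%, 38% of tested scans go to ICA and kappa goes from 0.64 to 0.77 or 0.78. A second simulation, with rates set to give about 36–38% ICA before any interpretation error, gave at reader SD 10: 0.74 to 0.83 with an identical call, 0.74 to 0.73 at 5% error and 0.74 to 0.65 at 10%.

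**The case against.** The strongest reply is that agreement on the combined test is a legitimate quantity. A shared, objective input is a real part of that test's reproducibility, not a contaminant. That stands, and it is why the combined kappa should stay.

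A reader might infer that one CT-FFR call is handed to both readers and overrides their stenosis calls, so that kappa must rise. The documents do not support that. The computation is shared, but Section 6.3 and the physician interpretation in Section 9 leave room for a separate CT-FFR call by each reader, and step 5 shows that the gain can then shrink or reverse. The override is also one-sided, because a negative CT-FFR leaves the reader's call in force. A reader who calls below 30% has no CT-FFR pathway, so disagreement can persist there.

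A reader might also infer that the sponsor will report a higher kappa as better reading. No section says so, and the stated objective is in terms of PPV and NPV. Nor does the plan say that the two kappas use different scans: a method for dependent kappas presupposes the same ones. The common set is simply not named.

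Finally, a CCTA kappa read blind to CT-FFR is already planned. What is missing is its role, and a limit on what the difference may be used to claim.

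**Conclusion.** The point holds conditionally. If one CT-FFR call serves both readers and both call at least 30%, agreement in CT-FFR-positive scans is fixed by the rule, and kappa can be expected to rise with no change in either reader. In CT-FFR-negative scans the combined result is essentially the reader's own CCTA call, with or without MPI. If each reader interprets CT-FFR separately, the change may be smaller or negative, and it mixes CT-FFR interpretation with stenosis reading. On neither reading does the difference show that CT-FFR helps less experienced readers.

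The size is illustrative. Anchored to 35% ICA, the independent-call formula gives rises of about 0.06 to 0.26 (0.60 to 0.66; 0.40 to 0.66). It rests on assumed CCTA positivity, assumed kappa, equal marginals and independence, none of which the plan supplies. The referral rule is taken from Section 8.3, which matches Section 9.2. Section 6.1 states the CT-FFR route to ICA only for 30–49%, and under that reading the override would cover fewer scans. Aim 2 is secondary and the Section 14.1 sample size does not depend on it, so this is a worthwhile, inexpensive correction and not a threat to the primary analysis.

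**What to change.** In Section 14.2, Aim 2:

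1. Keep the kappa on each reader's own CCTA reading, made before CT-FFR, as the reader-agreement result, and state how that reading is categorised. At present only the combined result has a positive/negative definition.
2. Keep the combined kappa, labelled as reproducibility of the combined test. Compute both kappas on the same scans, those with a CT-FFR result, and report them separately for CT-FFR-positive and CT-FFR-negative scans. If the call is shared, the combined kappa may be undefined in the positive stratum because every result is positive, so give raw agreement there as well.
3. State that the difference between the kappas will not be interpreted as reader improvement, and whether the CT-FFR call is made once per scan or by each reader.

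The reads are already planned, so the cost is some wording and one stratified table. The strata are smaller: on the planning figures, at most about 121 CT-FFR-positive scans and at least about 225 negative. The trial also gives up a claim that might look favourable but would not inform the reader objective.
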